ID: 2016036 Perioperative Administration of Tranexamic Acid for Placenta Previa and Accreta Study

Perioperative Administration of Tranexamic Acid for Placenta Previa and Accreta Study (TAPPAS): A Randomized, Placebo-controlled Double Blind Trial

UCSF Fresno Department of Obstetrics and Gynecology

Brief Synopsis

The purpose of this pilot study is to determine if intravenous tranexamic acid (TXA) is effective for reducing blood loss during high risk surgical procedures related to placenta previa and placenta accreta. TXA is currently used in other types of surgery for patients who are expected to have a large blood loss, such as orthopedic or cardiac surgery. The drug will be given AFTER delivery of the baby, so there is no risk of harm to the infant when participating in the study.

Background

Significance: The incidence of morbidly adherent placenta is rising due to increasing cesarean rates, and is currently estimated at 1 in 500 to 700 deliveries. Placenta accreta, a condition in which the placenta abnormally invades the uterine wall, carries a high risk of operative complications and often requires cesarean hysterectomy. Cesarean hysterectomy leads to higher intraoperative blood loss and morbidity when compared to a routine cesarean delivery. Retrospective reviews estimate there a 40% risk of requiring blood transfusion over ten units, and a 7% risk of maternal death (1).

Placenta accreta can be suspected antenatally based on certain risk factors, such as prior cesarean delivery and abnormal placenta location. For example, a woman with 3-4 prior cesarean deliveries and a placenta previa (low lying placenta) has a 60% risk of placenta accreta (14). Additional ultrasound and/or MRI studies can identify suspicious imaging features. However, diagnosis cannot be confirmed until the time of surgery, at which point abnormal placental behavior (hemorrhage, or failure of the placenta to detach) may be observed. The diagnosis is confirmed by final pathology report. Women with multiple prior cesarean sections, placenta previa, and placenta accreta have greater expected intraoperative blood loss, perioperative complications and morbidity than primary (first-time) cesarean sections (14).

Placenta accreta is as challenging to treat as it is to diagnose. The only commonly described innovation thus far is interventional radiology preoperative placement of balloon catheters in the uterine arteries to reduce intraoperative bleeding. Yet the evidence supporting this practice is mixed and in some series has not been shown to provide a statistically significant reduction in blood loss (2). Additionally, some motivated patients with accreta who wish to preserve the uterus do not undergo hysterectomy, and instead are given methotrexate after delivery to encourage absorption of the placenta. This approach frequently results in failure and hysterectomy at a later date. Current recommendations include referral of patients with a high suspicion of accreta to a tertiary care center for delivery, preparedness for a massive transfusion protocol if needed, and a planned, late preterm delivery to occur with coordinated support of surgical subspecialists (such as oncology backup) if bladder or other visceral organ involvement is suspected.

Innovation: To date, no novel or pharmacologic methods of reducing blood loss have been described for women at risk for placenta accreta. Intravenous tranexamic acid (TXA), a drug with

anti-fibrinolytic activity, is routinely used in elective orthopedic and cardiac surgery to reduce blood loss. Intravenous tranexamic acid is currently FDA approved for use in patients undergoing cardiac surgery or total knee arthroplasty or total hip arthroplasty to reduce peri- and postoperative blood loss and to reduce the need for blood transfusion. Although off label, the use of TXA in trauma patients with massive blood loss is also well described (3,4). The FDA states that prospective studies investigating the optimal use of tranexamic acid in trauma and other settings are needed and encouraged (5).

There has been growing interest in the application of tranexamic acid in obstetrics and gynecology. In multiple international studies, intravenous TXA has been shown to significantly reduce blood loss when given prophylactically with cesarean delivery or vaginal delivery without an increase in morbidity from adverse thrombotic events (6-9). Currently, a large, international (n=15,000) clinical trial is being conducted in middle- and low-income countries investigating the use of TXA for post-partum hemorrhage after vaginal delivery (10). A recent Danish study has also been completed regarding the use of TXA in benign gynecologic surgeries, i.e. routine hysterectomy (11). Furthermore, in March of 2016, Pacheco et al released new guidelines recommending the use of TXA in all obstetrical cases requiring massive transfusion protocol. TXA is recommended to be given in round three of obstetrical hemorrhage cases (1 gram intravenously over 10 minutes). (15). The authors called for more research to clarify the role and timing of administration of the drug in high risk obstetrical populations. Lastly, the 2015 Cochrane review of more than 3,000 obstetrical patients given TXA showed reduction in bleeding with no increase in adverse events including thromboembolism (16).

To date, TXA has not been studied in the particular population of patients requiring cesarean hysterectomy for placenta previa or accreta. This inexpensive, low risk medication has potential to greatly reduce perioperative morbidity and cost when used in a uniquely high risk obstetrical population.

Hypothesis

We predict tranexamic acid will reduce intraoperative bleeding associated with cesarean hysterectomy in patients with suspected placenta accreta compared to placebo. We aim to perform a pilot study showing a 25% reduction in estimated blood loss versus placebo.

Methods

Study design: This pilot study will be conducted as a randomized, placebo-controlled, double blind trial in the CRMC obstetrical department. The subjects will be recruited from outpatient clinics by the principal investigator or co-investigators during their routine antenatal care. Study consent will be secured during a routine antepartum outpatient visit, or sometimes during an antenatal admission to Labor and Delivery. The majority of patients at CRMC and CCMC with suspected placenta accreta are referred to the perinatologists at the Prenatal Diagnostic Center, and we anticipate most patients will be recruited from this practice. We will not attempt to recruit new patients who are in active labor, or those with medical acuity who require immediate intervention.

Study population: A consequence of studying pregnant women is that all of our study subjects will represent a vulnerable population. Based on our patient demographics, we anticipate a large proportion of the women in our study will be of Hispanic ethnicity, and will be preterm (before 37 weeks gestation). In general, patients with suspected placenta previa have a planned preterm delivery at 34-36 weeks.

Inclusion criteria:

- English and Spanish speaking pregnant

- Any order pregnancy (singleton, twin gestation, etc)

- With a suspected accreta based on ultrasound or MRI imaging studies

- All women evaluated for placenta accreta and deemed to be high risk for this disease (≥40% risk) ^{(14),} meaning women diagnosed with a placenta previa and greater than or equal to 2 prior c-sections

Exclusion criteria:

- Women less than 18 years of age

- Women with a personal history of venous or arterial thrombosis (deep vein thrombosis, pulmonary embolism, myocardial infarction, or stroke

- Women with a personal history of clotting disorder, such as anti-phospholipid syndrome
- Women who do not have a good understanding of either English or Spanish will be excluded.

- Women with defective color vision (color-blindness) [See Appendix A]

Pharmacy and Drug Delivery Protocol:

Drug purchasing: Per CRMC policy, the pharmacy cannot charge a patient for an approved drug in a research protocol. However, the CRMC pharmacy regularly purchases the study drug for use in surgical patients. The CRMC pharmacy has agreed to purchase the study drug for the principle investigator ([name]), and the studies' grant money will be used to reimburse the pharmacy at cost. Each vial of 1 gram of tranexamic acid for intravenous administration costs the pharmacy \$16.70. An initial box of ten vials has been purchased and additional boxes will be ordered after five patients are enrolled.

Randomization protocol: The drug and placebo will be stored, logged, and dispensed from the CRMC Inpatient Pharmacy. A recruited patient will be labeled study subject number one, and so on, by the study investigators. The name and study number will be given to Inpatient Pharmacy. Inpatient Pharmacy staff will randomize the subject to treatment or placebo using a blocked randomization technique and a computer protocol designed with assistance from [name]. The block size will be set at 4-6 to ensure that the number of treatment and placebo subjects are as close to equal as possible. Inpatient Pharmacy will assign that patient to receive drug or placebo prior to the scheduled surgery. The randomization assignments for each study subject will be located in a study binder in the research pharmacy space. Inpatient Pharmacy staff members will be the only unblinded study staff. The study investigators, clinicians, patient, and hospital staff will be blinded to treatment assignments.

Pharmacy and Drug Delivery Protocol:

Drug purchasing: Per hospital pharmacy policy, the study drug must be ordered from an outside pharmacy. The study drug will be purchased by the investigator from a non-CRMC pharmacy using her DEA number and delivered to the research pharmacy technician. The online pharmacy will be accredited with the National Association of Boards of Pharmacy member and recommended by chief hospital pharmacist.

Drug delivery: In orthopedic and cardiac surgery, 1 gram of intravenous TXA is routinely given 15 minutes before incision time. TXA is typically prepared at CRMC by removing 20cc of fluid from a small IV bag of 5% dextrose in plain water and then injecting the drug into the remaining 30 cc. This is then delivered with an IV piggyback with the patient's preoperative fluids.

In our study in pregnant patients, 1 gram intravenous TXA (or placebo) will be administered immediately after delivery of the infant and after clamping of the umbilical cord to avoid any potential fetal effects. The drug will be prepared and ready to hang at the beginning of the case.

Drug preparation will include the following: Removal of 20 ml from a 50 ml bag of D5W and injection of 10 milliliters of 100mg/ml TXA resulting in a final total volume of 40 ml. Placebo will be prepared by removing 10 ml from a 50 ml bag of D5W. The final volume of the study drug and the placebo bags will be the same and identical in appearance.

Anesthesia staff (physicians and nurse anesthetists) working in the trauma operating rooms will have an in-service about the research study and procedures at a weekly staff meeting to ensure proper education and compliance with study protocol. Intravenous TXA or placebo will be given to the randomized patients by CRMC anesthesia staff after the cord has been clamped and cut based on the intraoperative findings.

All patients undergoing cesarean at high risk for accreta at CRMC have two large bore IVs placed preoperatively. The patient will not require an additional IV for the study drug. TXA is delivered in 5% dextrose plain water and this can be hung as a piggyback with the patient's intraoperative fluids. TXA is clear and colorless and will be visually indistinguishable from the placebo. The hospital pharmacy will be able to provide the placebo.

Primary outcome: The primary endpoint will be estimated intraoperative blood loss (EBL), which is routinely recorded at the end of all operative cases. EBL is *estimated* by the operating room team following a discussion between the surgeon and anesthesia staff based on number of tapes / sponges used, amount of fluid in suction canister, amount of blood on the floor, etc. Secondary endpoints will include amount of blood transfusion, preop and post operative hemoglobin levels, length of hospital stay, ICU admission rates and length of stay, and post-operative complications (DVT, PE, surgical site infection). Maternal demographic information, medical comorbidities, and infant outcomes (weight, Apgar scores, NICU admission) will also be recorded with chart review.

The pilot trial is planned to last 24-36 months with possible extension if needed to meet study enrollment targets. All final results from the study will be submitted for publication in recognized peer-reviewed obstetrical journals. After completion of the pilot study, a future goal is to approach the Maternal Fetal Medicine Unit Network (MFMU) to organize a larger multi-center trial with additional academic centers (https://www.nichd.nih.gov/research/supported/Pages/mfmu.aspx). The MFMU is a national network established by the NIH to reduce maternal, fetal, and infant morbidity, and to provide the rationale for evidence-based, cost-effective obstetric practice.

Sample Size Calculation

Sample Size: Given the low incidence of placenta accreta at CRMC (approximately 10-15 cases per year), we propose performing a pilot / feasibility study that will include approximately 40 cases over the study period of 3 years. Prior studies using TA in elective cesarean deliveries and post-partum hemorrhage found a 30-33% reduction in estimated blood loss (9, 12). A power analysis with a conservative estimate of 25% reduction in predicted blood loss constraining type I errors to 95% and type II errors to 50% requires 29 patients in each sample given our known average and standard deviation of blood loss in accreta patients from the past year.

Statistical Analysis: Categorical data will be compared using the Chi-square test. Continuous variables, such as estimated blood loss, will be analyzed by comparing means using the Student t-test.

Adverse Events Monitoring (and explanation of routine patient care)

The principle investigator [name] does not typically scrub on planned cesarean hysterectomy cases. These surgeries are typically performed by UCSF faculty sub-specialists, [name] (oncology) or [name] [name] (Urogynecology). However, a coinvestigator (UCSF

resident) will be present in the operating room for all cases, and directly involved in patient care throughout the patient's hospitalization.

All UCSF generalists (including [name]) and residents (co-investigators) will be involved in the post operative care of these patients. There is an "attending of the day" for Labor & Delivery who rounds on high risk post partum patients with the residents and directly supervises resident care of these patients. A resident co-investigator will closely follow the patient throughout their post-operative course. Standard clinical care involves a "PM check" (evening visit to see the patient on the day of surgery), as well as daily morning rounding by a resident and attending faculty. *The principle investigator [name] will be notified of all potential adverse events by frequent communication with the resident team and with chart review, starting on post operative day zero, and continuing daily throughout the length of the patient's hospitalization.*

Patients will be called by the PI or a co-investigator 24-48 hours after discharge to evaluate for any clinical needs at home and to monitor for potential adverse events. Patients will be seen at 2 and 6 weeks post operatively in clinic (if their health insurance allows this) by a resident co-investigator and UCSF faculty which is standard for post partum / post surgical care. If a patient no-shows to a post partum visit, they will be called to ask them to reschedule, and a letter will be sent to the home address to improve follow up rates.

Patients will not be followed beyond the 6 week post partum visit. A copy of the consent form, including the drug risks, will be provided to each patient in the study to be given to their primary care doctor for future care.

If a significant adverse event occurs at any point during the study, the research pharmacy technician will be notified and that patient will be unblinded to the lead study investigator. The principle investigator will present the patient and adverse events to the safety monitoring committee for discussion and potential action in a timely fashion (within 48 hours for significant adverse events (blood clot, patient death) and within one week for minor adverse events (rash, nausea/vomiting).

Risks to Human Subjects

The proposed research activities qualify as Human Subjects Research and meet the definition of clinical research, as described fully below.

Potential Risks: Because TXA inhibits fibrinolysis, it carries a theoretical risk of thrombosis especially in patients with a previous history of thrombosis. However, large systematic reviews of randomized clinical trials for TXA use in elective surgical patients show no significant increase in the incidence of myocardial infarction, stroke, DVT, or pulmonary embolus (13). Furthermore, although pregnancy and the post partum period represent a hypercoagulable state, the risks of thrombosis in pregnancy are comparable to that of the orthopedic surgical population, in which TXA has well documented safety. TXA so far has not been shown to have any adverse effects in existing clinical trials involving pregnant women, and is currently being investigated in several large international trials in pregnant and post partum women to evaluate its promise in the treatment of post partum hemorrhage.

Please see Appendix A for the Lexicomp drug monograph with on and off label dosing, and risks of adverse events.

Breastfeeding: TXA is category B in pregnancy with no evidence of adverse events in pregnancy in animal studies. For comparison, TXA is safer than Tylenol use, which is category C with some evidence for adverse events in animal studies. TXA is compatible with breastfeeding.

Standard of Care: The current standard of care for patients with suspected accreta is to perform cesarean delivery at a tertiary care hospital with experienced surgical teams. Planned late preterm delivery at 34-36 weeks gestation is recommended. Patients are expected to have two large bore IVs placed and be typed and crossed for transfusion, with the ability to activate a massive transfusion protocol if needed. Depending on surgeon preference, preoperative prophylactic placement of balloons in the arteries leading to the uterus to attempt to lower blood loss may also be performed. Research participants will be receiving the standard of care regardless of whether they choose to participate in the study. By choosing to participate, a patient's regular treatment plan for placenta previa or placenta accreta is completed in addition to the administration of study drug at the time of surgery.

Confidentiality and Privacy: The patients' information will be accessed through electronic charts maintained by CRMC Health Information Management. The patients will only be identified by a non-identifying code assigned to their medical record number. This data will be stored on a password protected Excel spreadsheet, accessible only to IRB approved investigators, and maintained on the UCSF-Fresno secure server.

Data Security: The data will be saved on an Excel spreadsheet and the patients will only be identified by the non-identifying code. Protected health information will not leave the study site and only IRB approved investigators would have access to it. Any data leaving the secure study site or seen by investigators not approved by the IRB will be de-identified.

Conflicts of Interest

The PI has no conflicts of interest to report.

Funding

A research grant from CCFMG was awarded to assist with the completion of this project. The final budget is attached. The grant will assist with remuneration of study subjects, support staff, and statistical support. The study investigators will not receive any payment through the grant.

References

1. O'Brien JM, Barton JR, Donaldson ES. The management of placenta percreta:

conservative and operative strategies. Am J Obstet Gynecol. 1996;175(6):1632.

10.1016/j.thromres.2014.11.012. Epub 2014 Nov 20. Review. PubMed PMID: 25559460. 5. Verdun, N. Hemostatic Products CDER. FDA.

http://www.fda.gov/downloads/medicaldevices/newsevents/workshopsconferences/ucm41490 2.pdf Accessed 12/15/2015.

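### The entry criteria leave open whether suspicious imaging and high-risk history are alternatives or both required, and the power figure, randomization and EBL analysis make no provision for the resulting case mix

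*Combined protocol and SAP*

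**What the plan says.** All places are in the combined protocol and SAP.

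- **Methods, Inclusion criteria.** One bullet reads "With a suspected accreta based on ultrasound or MRI imaging studies". The next begins "All women evaluated for placenta accreta and deemed to be high risk for this disease" and defines this as a risk of at least 40%, meaning previa together with 2 or more prior cesareans. The conjunction inside the second bullet joins previa to the prior cesareans. Nothing joins the two bullets.
- **Hypothesis.** "We predict tranexamic acid will reduce intraoperative bleeding associated with cesarean hysterectomy in patients with suspected placenta accreta compared to placebo".
- **Background.** Accreta may be suspected from risk factors. The risk is put at 60% for previa with 3-4 prior cesareans. The diagnosis is settled only at surgery and by pathology.
- **Sample Size Calculation.** 29 per arm is needed for a 25% reduction, "given our known average and standard deviation of blood loss in accreta patients from the past year". Neither the mean nor the SD is printed. The same paragraph plans about 40 cases in total, from a caseload of 10-15 accreta cases a year.
- **Randomization protocol.** "The block size will be set at 4-6 to ensure that the number of treatment and placebo subjects are as close to equal as possible". No stratification factor is named.
- **Statistical Analysis.** Continuous outcomes such as EBL "will be analyzed by comparing means using the Student t-test". No covariate is named.

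**The concern.** The two readings of the list give two different trials. If both bullets must be met, a woman with imaging-suspected accreta but only one prior cesarean, or without previa, is ineligible, although she fits the hypothesis. If either bullet is enough, a woman with previa, 2 prior cesareans and unremarkable imaging is eligible. At the protocol's own threshold, up to 60% of women entering by that route might not have accreta. Several investigators recruit, so different readings would enrol different populations.

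The second reading also affects the statistics. The planning mean and SD come from accreta patients, and the documents do not say whether that means confirmed or suspected cases. If women entering by the two routes bleed differently, the between-group difference goes into the residual variance of an unadjusted t-test. In addition, unstratified blocks allow the routes to be unevenly split between arms of about 20. The trial is meant to lead to a larger multicentre study, so its variance estimate should belong to a population that can be described.

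**Working it through.** **Inputs from the documents:** 29 per arm; 25% reduction in mean EBL; 50% power; about 40 women planned, so about 20 per arm; 40% accreta risk as the floor of the risk-factor route.

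**Assumptions, because the documents are silent or unclear:** alpha 0.05 two-sided (the text speaks of "constraining type I errors to 95% and type II errors to 50" percent, read here as 95% confidence); the same 25% proportional effect in accreta and non-accreta women; a common SD in both arms; no dropout; accreta share *p*; ratio *r* of non-accreta to accreta mean EBL.

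**Step 1: the plan's own figure.** With no mean or SD printed, 29 cannot be reproduced forwards. Solving the noncentral-t power equation for 50% power at 29 per arm gives a standardized difference of 0.524, so CV = 0.25 / 0.524 = 0.477 (0.572 if one-sided). The figure of 29 is therefore attainable but cannot be verified.

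**Step 2: a mixed population.** Set the accreta mean to 1 and give both groups a CV of 0.477.

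- Mean: m = p + (1 − p)r
- Variance: v = p·0.477² + (1 − p)(0.477r)² + p(1 − p)(1 − r)²

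Example with p = 0.4, r = 0.5: m = 0.70; v = 0.0912 + 0.0342 + 0.0600 = 0.185; SD 0.430; CV 0.430/0.70 = 0.615. Power at 29 per arm is 33%.

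| Power at 29 per arm | r = 1/3 | r = 1/2 | r = 0.7 | r = 1 |
|---|---|---|---|---|
| p = 0.4 | 23% | 33% | 44% | 50% |
| p = 0.6 | 28% | 36% | 45% | 50% |
| p = 0.8 | 36% | 41% | 47% | 50% |

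**Step 3: sensitivity to the equal-CV assumption.** If non-accreta CV is 0.25 with p = 0.4 and r = 0.7, power at 29 per arm is 56%, above the stated value. At r = 1/2 and p = 0.4, even zero spread among non-accreta women leaves a CV of √(0.0912 + 0.0600)/0.70 = 0.56, so there power stays below 50%. The direction depends on inputs that are not in the documents.

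**Step 4: the planned size.** At 20 per arm and CV 0.477, with every woman having accreta, power is about 36%. With r = 1/2 and p = 0.4 or 0.6 it is about 24% or 26%. Removing the between-group term p(1 − p)(1 − r)² from v, as full adjustment for true accreta status would, gives about 33% or 34%. Entry route is only a proxy for accreta, so this is an upper bound on what adjusting for route can recover.

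**Step 5: chance imbalance.** With 16 accreta cases among 40 women split 20/20, the hypergeometric probability that the arms differ by 4 or more cases is 33%. A 4-case difference shifts the difference in mean EBL by (4/20)(1 − r)/m, which is 22%, 14% or 7% of the overall mean for r = 1/3, 1/2 or 0.7.

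**The case against.** A reader might infer that the stated 50% power is shown to be overstated. The documents do not support that.

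- They give neither the case mix nor the blood loss of women without accreta. The Background sentence on greater expected loss compares women with multiple cesareans, previa and accreta with women having a first cesarean. It does not compare accreta with previa alone.
- The source group of accreta patients is undefined. If it means women managed as suspected accreta, the gap between planning and enrolled populations narrows.
- 40% is the floor for one route, not the expected share overall. The protocol expects most recruits from the practice that receives suspected-accreta referrals.
- Equal means leave power unchanged, and a smaller non-accreta CV can raise it.

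All of this stands, and it limits the power figures to illustration.

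Two other inferences also fail. Unstratified blocks do not make a power figure wrong, because chance imbalance is already within the t-test's error. Nor does a 4-case imbalance match the 25% target: it gives 7-22%. At a 40% accreta share, reaching 25% takes a ratio of 1/3 and a 6-case imbalance, which has a probability of about 11%.

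Finally, it is fair to say that the plan's larger power problem is enrolling about 40 women against the 58 (2 × 29) that its own calculation requires. That shortfall is separate, and any case-mix effect would come on top of it.

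None of this answers the ambiguity in the entry list, which needs no assumption to establish.

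**Conclusion.** The point holds as a defect of definition with a possible, unproven cost in precision. The criteria do not settle who is eligible. Each reading has a problem: one sits badly with the hypothesis, and the other admits women whom the planning figures may not describe. Even on the joint reading some enrolled women will not have accreta, since confirmation comes only at or after surgery.

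The statistical cost arises only if blood loss differs between the groups. Across the assumed ratios and accreta shares with equal CVs, power at 29 per arm runs from 23% to 47%. It is 50% at equal means and can exceed that with a less variable non-accreta group. All of these values rest on a CV inferred from the sample size, not on printed data. Whatever the case mix, the 50% figure applies to 29 per arm and not to the roughly 20 per arm planned.

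**What to change.** 1. The investigators state whether the two bullets are alternatives or jointly required, and bring the criteria and the hypothesis into line. The documents do not settle which is meant, so this is their decision. Cost: one line.
2. If the bullets are alternatives, the pharmacy runs its blocked list in two strata, imaging-suspected and risk-factor-only, and entry route is prespecified as a covariate in the EBL analysis. Cost: a second list and one model term. Incomplete blocks in each stratum can leave a small overall imbalance (at most 3 women per stratum with blocks of 6). Balance on true accreta status is improved only as far as route predicts it.
3. Print the planning mean and SD, and define the women they came from. Recompute both from past patients at the site who meet the clarified criteria, and restate power at the planned total of about 40. Cost: a chart pull of routinely recorded EBL. The restated power may look less favourable. No additional women need to be enrolled.

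### The only power analysis asks for 29 women per arm (58) at 50% power and gives the type I error as 95%, but about 40 women are planned and no power or precision is stated for 40

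*Combined protocol and SAP*

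**What the plan says.** Under Sample Size Calculation the protocol cites the low local incidence, 10-15 cases a year, and continues: "we propose performing a pilot / feasibility study that will include approximately 40 cases over the study period of 3 years". The randomization protocol aims for near-equal arms, so this means about 20 per arm.

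The same paragraph then reports a power analysis for a 25% reduction: "constraining type I errors to 95% and type II errors to 50% requires 29 patients in each sample". Its inputs are described only in words, as "given our known average and standard deviation of blood loss in accreta patients from the past year"; the values themselves appear nowhere in the document. Under Statistical Analysis, continuous variables such as blood loss "will be analyzed by comparing means using the Student t-test"; sidedness is not stated.

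The Hypothesis section says: "We aim to perform a pilot study showing a 25% reduction in estimated blood loss versus placebo". The paragraph on trial duration says the pilot is "planned to last 24-36 months with possible extension if needed to meet study enrollment targets", without giving the target as a number.

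**The concern.** Two sample sizes stand in one paragraph and nothing connects them. The power statement describes a trial 45% larger than the one planned (58/40 = 1.45). A reader who takes it at face value would credit the trial with 50% power, which about 40 women do not provide on the plan's own terms.

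The error rate is also impossible as written. A two-sided test at a 95% level rejects at least 95% of the time even when there is no effect, so its type II error is at most 5% and cannot be 50%. With the mean, SD and sidedness missing as well, the calculation cannot be repeated.

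The stake is interpretation. The pilot is described as a step towards a larger multi-center trial. Without power or precision for the planned size, a reader cannot judge how informative it will be, and a non-significant result could be mistaken for evidence against benefit.

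**Working it through.** **Inputs from the protocol.** 29 per arm; type II error 50%; 25% reduction; about 40 women in near-equal arms, so n = 20 per arm; Student t-test; 10-15 cases a year.

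**Assumptions.** Type I error 5%; both sidedness options tried; equal SDs unless stated otherwise.

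**1. Can 29 be reproduced?** No. The normal-approximation formula is n = 2(z_α + z_power)² / d², with d = 0.25 × mean / SD, and the mean and SD are not given. For a two-sided 5% test at 50% power, 29 corresponds to an SD/mean of about 0.49. Assumed values show how much depends on the missing figures (two-sided, 25% reduction):

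| Assumed SD/mean | n per arm for 50% power | Power at 20 per arm |
|---|---|---|
| 0.4 | 20 | 51% |
| 0.5 | 31 | 35% |
| 0.6 | 45 | 26% |
| 0.8 | 79 | 17% |

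**2. The 95% taken literally.** With SD/mean 0.49, a two-sided level of 0.95 and 50% power, the formula gives about 1 patient per arm. The 95% is therefore a misstatement.

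**3. Power at 20 per arm, if 29 per arm gives 50% power.** At 50% power z_power = 0, so d = z_α × √(2/29) = z_α × 0.2626. Power at 20 per arm is Φ(d × √(20/2) − z_α).

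- Two-sided: d = 1.960 × 0.2626 = 0.515; power = Φ(1.628 − 1.960) = Φ(−0.332) = 37.0%.
- One-sided: d = 1.645 × 0.2626 = 0.432; power = Φ(1.366 − 1.645) = Φ(−0.279) = 39.0%.
- With the noncentral t instead: d = 0.524 and power 36.5% two-sided; d = 0.437 and power 38.7% one-sided.

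So roughly 36-39%, moving by about a point if 29 had been rounded up.

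**4. If the treated arm's SD falls in proportion to its mean.** Take 29 as derived from the single historical SD, and give the treated arm 0.75 of that SD. In units of the placebo SD, the standard error at 20 per arm falls from √(2/20) = 0.316 to √((1 + 0.75²)/20) = 0.280. Simulation (200,000 trials, normal data) gives about 45% power two-sided and 46% one-sided. If 29 was itself derived with proportional SDs, power returns to about 36.5%.

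**5. Precision.** The 95% CI half-width for the difference in means is t(0.975, 2n − 2) × √(2/n) × SD.

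- n = 20: 2.024 × 0.3162 = 0.640 SD.
- n = 29: 2.003 × 0.2626 = 0.526 SD.

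In SD units this needs neither the mean nor the SD. The interval at 20 per arm is about 22% wider (0.640/0.526 = 1.22).

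**6. Accrual.** Three years at 10-15 cases a year gives 30-45 women, which covers 40 but not 58. Reaching 58 would take 58/15 = 3.9 to 58/10 = 5.8 years.

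**The case against.** The strongest reply is that this is openly a pilot. The protocol calls it one, gives low incidence as the reason for about 40, prints 29 per arm in the same paragraph, leaves room to extend, and looks to a later multi-center trial. A design that accepts 50% power at 29 per arm loses only about 11-14 points at 20 (50% to 36-39%), or about 5 if SDs shrink with the mean. The 95% is most naturally a slip for 95% confidence. Much of this stands: it explains why 40 was chosen and is a good reason not to ask for more women. It does not supply power or precision for 40, the extension clause names no target above 40, and the error rate still needs correcting.

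Three stronger readings are tempting and are not supported.

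- *That 29 is wrong.* The inputs are not printed. With an SD/mean of 0.4, 20 per arm would already give about 50% power.
- *That the trial has only an even chance if the true reduction is as large as in the cited studies.* The plan says these "found a 30-33% reduction in estimated blood loss". With equal SDs, power at 20 per arm is about 49% at 30% and 56-57% at 33%, but with SDs proportional to the mean it is about 60-61% and 68-71%. The statement is not robust. One of the two references behind that range is also listed as a study protocol.
- *That the trial is set up to fail its aim.* The documents define no success criterion, and the word showing in the Hypothesis is not tied to a significance threshold.

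**Conclusion.** The point holds. The sample-size paragraph states a size that the planned trial does not deliver and an error rate that is impossible as written, and it gives no power or precision for the trial that will be run. None of this depends on an assumption.

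The size of the shortfall does. If 29 per arm gives 50% power at a 5% level, about 20 per arm gives roughly 36-39% for a true 25% reduction with equal SDs, or about 45% if the treated arm's SD shrinks with its mean; either way it is below 50%. The CI half-width of about 0.64 SD against 0.53 SD assumes only a common SD and 20 or 29 per arm.

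A reader might infer that the trial must recruit 58 women. The documents do not support that: feasibility is a legitimate ground for 40, provided it is stated as the ground and its consequences are given.

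**What to change.** Keep about 40 women, the endpoint and the Student t-test.

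In the Sample Size Calculation:

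1. Give the type I error as 5% and state whether the test is one- or two-sided.
2. Print the mean and SD of blood loss used, and say whether they come from confirmed or suspected accreta. Eligibility rests on suspicion or risk, and the Background says diagnosis cannot be confirmed until surgery, so the two groups may differ.
3. Recompute the number per arm needed for a 25% reduction at a 50% type II error.
4. State that about 40 was chosen for feasibility and, if the recomputed number per arm exceeds 20, that 40 is below the required size.
5. Give the power for a 25% reduction and the expected 95% CI half-width for the difference in mean blood loss at about 20 per arm.

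Suggested wording: *Type I error 5%, (one-/two-)sided. Mean EBL in (confirmed/suspected) accreta patients in the past year was ___ (SD ___). A 25% reduction with a type II error of 50% would need ___ per arm. About 40 women (about 20 per arm) was chosen for feasibility (and is below that size). With about 20 per arm, power for a 25% reduction is ___% and the expected 95% CI half-width for the difference in mean EBL is ___.*

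The blanks should be filled from the sponsor's own mean and SD; the figures above are conditional illustrations.

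In the Hypothesis section, state the aim as estimating the difference in mean EBL with a 95% CI, with 25% as the design assumption.

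The cost is protocol wording and one recalculation from data the sponsor says it has, with no extra patients. The stated power is likely to become less favourable, and the aim moves from showing an effect to estimating it.
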